6.5 Follow-up (2 Weeks and 4 Weeks After End of Study Drug Treatment)

6.5.1 Follow-up 2 Weeks After End of Study Drug Treatment

The following procedures will be performed at the follow-up visit 2 weeks after EOST:

- Collect blood cultures for *Candida* spp.
- Collect other cultures and histopathology from other sites, as clinically indicated
- Perform imaging tests as clinically indicated to monitor the site(s) and extent of invasive candidiasis infection
- Record vital signs, including temperature, blood pressure, heart rate, respiratory rate, oxygen saturation, and weight
- Intravascular catheter management log, as clinically indicated
- Perform clinical laboratory assessments (serum chemistry, hematology, coagulation and urinalysis)
- Perform urine pregnancy test (for females of childbearing potential only)
- Perform neurological examination
- Perform focused, symptom-based physical examination, as clinically indicated
- Collect plasma sample for PK (APX001 [prodrug] and APX001A [active moiety]). Plasma samples for PK will be collected at the same time as samples are collected for the study's clinical laboratory assessments.
- Evaluate treatment outcome
- Record concomitant medications
- Assess adverse events

6.5.2 Follow-up 4 Weeks After End of Study Drug Treatment

The following procedures will be performed at the follow-up visit 4 weeks after EOST:

- Collect blood culture for *Candida* spp.
- Collect other cultures and histopathology from other sites, as clinically indicated
- Perform imaging tests as clinically indicated to monitor the site(s) and extent of invasive candidiasis infection
- Perform dilated fundoscopic examination (only required in those patients who had baseline positive fundoscopic findings [up to Day 3] or as clinically indicated)
- Intravascular catheter management log, as clinically indicated
- Record vital signs, including temperature, blood pressure, heart rate, respiratory rate, oxygen saturation, and weight
- Perform clinical laboratory assessments (serum chemistry, hematology, and urinalysis)
- Perform 12-lead ECG
- Perform urine pregnancy test (for females of childbearing potential only)
- Perform neurological examination
- Perform focused, symptom-based physical examination, as clinically indicated
- Evaluate treatment outcome
- Record concomitant medications
- Assess adverse events

6.5.3 Early Termination Visit and Withdrawal Procedures

For patients who are withdrawn from the study prior to completion, all EOST procedures will be performed at an Early Termination visit. These procedures include the following:

- Collect blood culture for *Candida* spp.
- Collect other cultures and histopathology from other sites, as clinically indicated
- Perform imaging tests as clinically indicated to monitor the site(s) and extent of invasive candidiasis infection
- Perform dilated fundoscopic examination (only required in those patients who had baseline positive fundoscopic findings [up to Day 3], or as clinically indicated)
- Intravascular catheter management log, as clinically indicated
- Record vital signs, including temperature, blood pressure, heart rate, respiratory rate, oxygen saturation, and weight

- Perform clinical laboratory assessments (serum chemistry, hematology, coagulation and urinalysis)
- Perform 12-lead ECG
- Perform urine pregnancy test (for females of childbearing potential only)
- Perform neurological examination
- Perform focused, symptom-based physical examination, as clinically indicated
- Collect plasma sample for PK (APX001 [prodrug] and APX001A [active moiety])
- Collect serum sample for analysis of(1,3)- β -D-glucan
- Evaluate treatment outcome
- Record concomitant medications
- Assess adverse events

7 EFFICACY ASSESSMENTS

7.1 Primary Efficacy Endpoint

The primary efficacy parameter is percentage of patients with Treatment Success at EOST as determined by the Data Review Committee (DRC).

7.2 Secondary Efficacy Endpoints

The secondary efficacy parameters include the following:

- Time to first negative blood culture
- Percentage of patients with successful Mycological Outcomes at EOST, and at 2 and 4 weeks after EOST
- Percentage of patients with Treatment Success at EOST as determined by the investigator
- Percentage of patients with Treatment Success 2 and 4 weeks after EOST, as determined by the investigator and by the DRC
- All-cause mortality at Study Day 30
- Number of patients with TEAEs

7.3 Exploratory Efficacy Endpoint

The exploratory efficacy parameters include the following:

- Change in serum (1,3)- β -D-glucan levels from Baseline (pre-dose) to EOST

7.4 Definitions for Efficacy Assessments

7.4.1 At End of Study Drug Treatment

Treatment Success is defined as meeting all of the following criteria:

- Two consecutive blood cultures negative for *Candida* spp. and/or for patients with a deep-seated site of infection, at least one negative tissue culture or aspirate/fluid
 - for patients with a deep-seated site of infection involving visceral organs from which a tissue culture is not obtainable, resolution of the attributable clinical signs of infection recorded at Baseline, and, as applicable, radiological improvement associated with the site of infection is required
- Alive at EOST
- No concomitant use of any other systemic antifungal therapies through EOST

Note: administration of another systemic antifungal immediately following EOST for suspected or documented *Candida* infection at any site does not constitute a treatment success at EOST

Treatment Failure is defined as any case that does not meet the criteria for Treatment Success.

Successful Mycological Outcome:

- Eradication is defined as a negative blood (and/or other infection site) culture(s) for *Candida* spp. in the absence of concomitant antifungal therapy through EOST
- Presumed Eradication (applicable to invasive candidiasis) is defined as clinical resolution of invasive *Candida* spp. infection where tissue samples are unavailable (supported by evidence of resolution/improvement in the diagnostic parameters used at Baseline)

Both of the above definitions are in the absence of concomitant or additional systemic antifungal therapy.

7.4.2 At Follow-Up (2 Weeks and 4 Weeks After End of Study Drug Treatment [EOST])

- Treatment Success (sustained) is defined as having met the criteria for Treatment Success at EOST with no change during the follow-up period
- Relapse is defined as re-occurrence of *Candida* in blood culture, or from other infection sites, during the Follow-up Period, or diagnostic parameters indicative of recurrence or late spread of the *Candida* infection
- Other:
 - Death
 - Unavailable for follow-up, or unevaluable at follow up for other reasons

Additional DRC assessment categories are provided in the DRC Charter

Mycological Recurrence is defined as mycologically confirmed infection based on blood culture (or other specimen(s) cultured from a normally sterile site), with the same Baseline *Candida* spp. during the 4 weeks after EOST.

7.5 Microbiological Assessments

7.5.1 Blood Cultures

For patients with candidemia, *Candida auris* confirmed in blood culture is required for qualification into the study, which must occur within 120 hours of the collection of the indicative positive blood sample. The study site's local microbiology laboratory will analyze blood and other cultures for *Candida* spp. Isolates of all *Candida* spp from SOC eligibility cultures must be submitted to the mycology reference laboratory for confirmation of identification and susceptibility testing.

For all patients (candidemia or invasive candidiasis), once consent is obtained, the first blood collection should comprise two consecutive sets (1 aerobic and 1 anaerobic blood culture bottle in each set) of blood cultures from 2 separate IV sites (1 from a central venous catheter (CVC) and 1 peripheral, or 2 peripherals if CVC is not applicable); a minimum of 1 set (1 aerobic and 1 anaerobic blood culture bottle in each set) of blood cultures is required thereafter.

Blood cultures for *Candida* spp. will be performed during the Screening period (daily), at Baseline (pre-dose), during Study Drug Treatment, at EOST, and 2 and 4 weeks after EOST, or Early Termination. During the Study Drug Treatment Period, blood cultures are required daily on Study Days 1 through 4; thereafter, blood cultures during study drug treatment may be stopped after negative results on 2 consecutive blood culture tests are obtained.

The study site's local microbiology laboratory will analyze all blood cultures for *Candida* spp. The local microbiology lab will send all *Candida* isolates from blood cultures to the mycology reference laboratory for confirmation of identification and susceptibility testing.

In the event that the study site uses a rapid diagnostic test for the diagnosis of candidemia, subsequent confirmatory blood cultures are required, and resulting isolates should be submitted to the mycology reference laboratory for confirmation of identification and susceptibility testing. Results from rapid diagnostic tests performed must be captured in the eCRF.

7.5.2 Cultures from Other Sites of Infection

For patients with invasive candidiasis, a tissue culture or aspirate/fluid sample confirmed positive for *Candida auris* that has been collected aseptically from a normally sterile site is required for inclusion in the study. Study qualification will occur within 168 hours of a confirmed positive tissue culture or aspirate/fluid collection. Isolates of all *Candida* spp. from SOC eligibility cultures and baseline and follow-up cultures must be submitted to the mycology reference laboratory for confirmation of identification and susceptibility testing. Tissue culture or aspirate/fluid samples

for *Candida* spp. will be collected at Baseline (pre-dose), and where amenable to sampling during Study Drug Treatment, at EOST, and 2 and 4 weeks after EOST, or Early Termination. Collection of culture or aspirate/fluid samples may be stopped after at least one negative tissue culture or aspirate/fluid sample.

The study site's local microbiology laboratory will analyze all tissue cultures or aspirate/fluid samples for *Candida* spp. The local microbiology lab will send all *Candida* isolates from tissue cultures or aspirate/fluid cultures to the mycology reference laboratory for confirmation of identification and susceptibility testing.

7.5.3 Intravascular Catheter Management and Log

If possible, all intravascular catheters should be removed and the catheter tips cultured by the local microbiology laboratory within 24 hours of APX001 dosing. The entrance site should also be cultured by the local microbiology laboratory if it appears infected. The local microbiology lab will send all *Candida* isolates from intravascular catheter or entrance site cultures to the mycology reference laboratory for confirmation of identification and susceptibility testing. Intravascular catheter management should be managed at the site level as per local SOC.

8 SAFETY ASSESSMENTS

8.1 Adverse Events

An adverse event is defined as any untoward medical occurrence in a clinical investigation subject administered a pharmaceutical product, which does not necessarily have a causal relationship with this treatment. An adverse event can therefore be any unfavorable and/or unintended sign (including an abnormal laboratory finding), symptom, or disease temporally associated with the use of a study drug, whether or not related to the study drug. All adverse events, including observed or volunteered problems, complaints, or symptoms, are to be recorded on the appropriate eCRF.

Adverse events, which include clinical laboratory test variables, will be monitored and documented from the time of informed consent until study participation is complete. Subjects should be instructed to report any adverse event that they experience to the Investigator. Beginning with Day 1 of study drug, Investigators should make an assessment for adverse events at each visit and record the event on the appropriate adverse event eCRF.

Wherever possible, a specific disease or syndrome rather than individual associated signs and symptoms should be identified by the Investigator and recorded on the eCRF. However, if an observed or reported sign or symptom is not considered a component of a specific disease or syndrome by the Investigator, it should be recorded as a separate adverse event on the eCRF. Additionally, the condition that led to a medical or surgical procedure (e.g., surgery, endoscopy, tooth extraction, or transfusion) should be recorded as an adverse event, not the procedure.

Any medical condition already present at Screening should not be reported as an adverse event unless the medical condition or signs or symptoms present at Baseline changes in severity or seriousness at any time during the study. In this case, it should be reported as an adverse event.

Clinically significant abnormal laboratory or other examination (e.g., ECG) findings that are detected during the study or are present at Screening and significantly worsen during the study should be reported as adverse events. The Investigator will exercise his or her medical and scientific judgment in deciding whether an abnormal laboratory finding or other abnormal assessment is clinically significant. Clinically significant abnormal laboratory values occurring during the clinical study will be followed until repeat tests return to normal, stabilize, or are no longer clinically significant. Any abnormal test that is determined to be an error does not require reporting as an adverse event. A laboratory finding that is abnormal but not clinically significant (e.g., does not warrant intervention) is not considered an adverse event.

8.1.1 Adverse (Drug) Reaction

All noxious and unintended responses to a study drug related to any dose should be considered an adverse drug reaction. “Responses” to a study drug means that a causal relationship between a study drug and an adverse event is at least a reasonable possibility, i.e., the relationship cannot be ruled out.

Drug-induced liver injury is defined in [Appendix D](#), and requires study drug withdrawal.

8.1.2 Unexpected Adverse Drug Reaction

An unexpected adverse drug reaction is defined as an adverse reaction, the nature or severity of which is not consistent with the applicable product information. For APX001, the reference safety information is included in the Investigator’s Brochure (IB) currently in force. The reference safety information will be reviewed yearly and the periodicity of the review will be harmonized with the reporting period of the Development Safety Update Report.

8.1.3 Assessment of Adverse Events by the Investigator

The Investigator will assess the severity (intensity) of each adverse event and will also categorize each adverse event as to its potential relationship to study drug using the categories of “yes” or “no.”

Assessment of Severity:

The severity of all adverse events should be graded according to the Common Terminology Criteria for Adverse Events (CTCAE) v4.03. These criteria can be found at <http://ctep.cancer.gov/reporting/ctc.html>. For those adverse events not listed in the CTCAE, the following grading system should be used:

- Mild (CTCAE Grade 1): Transient symptoms, awareness of sign/symptom, but easily tolerated and no interference with patient’s daily activities

- Moderate (CTCAE Grade 2): Marked signs/symptoms that interfere with patient's usual activities, but still acceptable
- Severe (CTCAE Grade 3): Incapacitating signs/symptoms which cause considerable interference with the patient's daily activities, unacceptable
- Life-threatening (CTCAE Grade 4): Life threatening or disabling adverse event
- Death (CTCAE Grade 5): Death-related adverse event

Causality Assessment:

The relationship of an adverse event to the administration of the study drug is to be assessed according to the following definitions:

No (unrelated, not related, no relation) – The time course between the administration of study drug and the occurrence or worsening of the adverse event rules out a causal relationship and another cause (concomitant drugs, therapies, complications, etc.) is suspected.

Yes (related) – The time course between the administration of study drug and the occurrence or worsening of the adverse event is consistent with a causal relationship and no other cause (concomitant drugs, therapies, complications, etc.) can be identified.

The definition implies a reasonable possibility of a causal relationship between the event and the study drug. This means that there are facts (evidence) or arguments to suggest a causal relationship.

The following factors should also be considered:

- The temporal sequence from study drug administration-
 - The event should occur after the study drug is given. The length of time from study drug exposure to event should be evaluated in the clinical context of the event
- Underlying, concomitant, intercurrent diseases-
 - Each report should be evaluated in the context of the natural history and course of the disease being treated and any other disease the patient may have
- Concomitant drug-
 - The other drugs the patient is taking or the treatment the patient receives should be examined to determine whether any of them might be recognized to cause the event in question
- Known response pattern for this class of study drug-
 - Clinical and/or preclinical data may indicate whether a particular response is likely to be a class effect

- Exposure to physical and/or mental stresses-
 - The exposure to stress might induce adverse changes in the recipient and provide a logical and better explanation for the event
- The pharmacology and PK of the study drug-
 - The known pharmacologic properties (absorption, distribution, metabolism, and excretion) of the study drug should be considered

8.2 Serious Adverse Events

An adverse event or adverse reaction is considered serious if, in the view of either the Investigator or Sponsor, it results in any of the following outcomes:

- Death
- A life-threatening adverse event
 - An adverse event or adverse reaction is considered “life-threatening” if, in view of either the Investigator or Sponsor, its occurrence places the patient at immediate risk of death. It does not include an event that, had it occurred in a more severe form, might have caused death
- Requires hospitalization or prolongation of existing hospitalizations
 - Any hospital admission with at least 1 overnight stay will be considered an inpatient hospitalization. An emergency room visit without hospital admission will not be recorded as a SAE under this criterion, nor will hospitalization for a procedure scheduled or planned before signing of informed consent. However, unexpected complications and/or prolongation of hospitalization that occur during elective surgery should be recorded as adverse events and assessed for seriousness. Admission to the hospital for social or situational reasons (i.e., no place to stay, live too far away to come for hospital visits) will not be considered inpatient hospitalizations
- A persistent or significant disability/incapacity or substantial disruption of the ability to conduct normal life functions
- A congenital anomaly/birth defect
- An important medical event
 - Important medical events that may not result in death, be life-threatening, or require hospitalization may be considered an SAE when, based upon appropriate medical judgment, they may jeopardize the patient and may require medical or surgical intervention to prevent one of the outcomes listed above. Examples of such medical events include allergic bronchospasm requiring intensive treatment in an emergency room or at home, blood dyscrasias or convulsions that do not result in inpatient hospitalizations, or the development of drug dependency

8.3 Serious Adverse Event Reporting – Procedures for Investigators

Initial Reports

All SAEs occurring from the time of informed consent until 30 days following the last administration of study drug must be reported to [REDACTED] safety within 24 hours of the knowledge of the occurrence (this refers to any adverse event that meets any of the aforementioned serious criteria). All SAEs that the Investigator considers related to study drug occurring after the 30-day follow-up period must be reported to the Sponsor.

To report the SAE, the Investigator must complete the SAE form electronically in the electronic data capture (EDC) system for the study. When the form is completed, [REDACTED] personnel will be notified electronically and will retrieve the form. If the event meets seriousness criteria and it is not possible to access the EDC system, the Investigator should send an e-mail to [REDACTED]

[REDACTED] fax number listed below) within 24 hours of awareness. When the EDC system becomes available, the SAE information must be entered within 24 hours of the system becoming available.

[REDACTED]
[REDACTED]
[REDACTED]

Follow-Up Reports

The Investigator must continue to follow the patient until the SAE has subsided or until the condition becomes chronic in nature, stabilizes (in the case of persistent impairment), or the patient dies.

Within 24 hours of receipt of follow-up information, the Investigator must update the SAE form electronically in the EDC system for the study and submit any supporting documentation (e.g., patient discharge summary or autopsy reports) to [REDACTED] via fax or e-mail. If it is not possible to access the EDC system, refer to the procedures outlined above for initial reporting of SAEs.

8.4 Expedited Reporting

The Sponsor will comply with all country-specific regulations relating to safety reporting to the regulatory authority, Institutional Review Board (IRB)/Independent Ethics Committee (IEC), and Investigators.

The Sponsor will report all relevant information about suspected unexpected serious adverse reactions that are fatal or life-threatening as soon as possible to the Food and Drug Administration (FDA), applicable competent authorities in all the Member States concerned, and to the Central Ethics Committee, and in any case no later than 7 days after knowledge by the Sponsor of such a case, and that relevant follow-up information will subsequently be communicated within an additional 8 days.

All other suspected unexpected serious adverse reactions will be reported to the FDA, applicable competent authorities concerned, and to the Central Ethics Committee as soon as possible but within a maximum of 15 days of first knowledge by the Sponsor.

The Sponsor will also inform all Investigators as required.

8.5 Stopping Rules

8.5.1 Study Stopping Rule

At any time, the independent DSMB may temporarily suspend enrollment until any significant safety concerns are resolved or terminate the study to ensure patient safety, if in the opinion of the DSMB, further dosing would pose an inappropriate safety risk. Guidelines for what constitutes inappropriate safety risks are described in the DSMB Charter.

Additionally, the study may be discontinued for any of the following reasons: five or more subjects in study (cumulative) experience a same Grade 2 (or higher) related AE (laboratory or systemic) which is coded in the same high-level group term per MedDRA coding, throughout the duration of study; lack of investigational product availability; inability to enroll the study; or decision by a regulatory authority or the sponsor.

8.5.2 Subject Stopping Rule

Study treatment for an individual patient may be discontinued for any adverse event, SAE, laboratory abnormality, or intercurrent illness which, in the opinion of the Investigator, indicates that continued dosing in the study is not in the best interest of the patient.

8.6 Pregnancy Reporting

A urine pregnancy test will be performed at Screening and Baseline (pre-dose), every 30 days during treatment if required by local regulations, EOST, and 2 and 4 weeks after EOST, or Early Termination for all female patients of childbearing potential. If the patient or partner of a patient participating in the study becomes pregnant during the study or within 30 days of discontinuing study drug, the Investigator should report the pregnancy to [REDACTED] within 24 hours of being notified. [REDACTED] will then forward the Exposure In Utero Form to the Investigator for completion.

A patient becoming pregnant while on study drug will immediately be withdrawn from the study and Early Termination study procedures will be performed.

The patient or partner should be followed by the Investigator until completion of the pregnancy. If the pregnancy ends for any reason before the anticipated date, the Investigator should notify [REDACTED]. At the completion of the pregnancy, the Investigator will document the outcome of the pregnancy within 24 hours. If the outcome of the pregnancy meets the criteria for immediate classification as an SAE (i.e., postpartum complication, spontaneous abortion, stillbirth, neonatal death, or congenital anomaly), the Investigator should follow the procedures for reporting an SAE.

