3 STUDY DESCRIPTION

3.1 Summary of Study Design

This is a multicenter, open-label, non-comparative, single-arm study to evaluate the efficacy and safety of APX001 for the treatment of candidemia and/or invasive candidiasis caused by *C. auris* in patients aged 18 years and over who have limited antifungal treatment options. The Study Drug Treatment Period will be up to a maximum of 42 days (inclusive of the loading dose [Study Day 1]). There will be a Follow-up Period of 4 weeks (+4 days) after EOST. The total duration of participation in the study is up to approximately 10.5 weeks (inclusive of the Screening Period [\leq 168 hours prior to Baseline]). Patients must have had *C. auris* confirmed in culture $<$ 120 hours (for candidemia) or $<$ 168 hours (for invasive candidiasis without candidemia) prior to qualification and dosing in the study.

Screening and Baseline procedures will be performed within no more than 120 hours (for candidemia) or 168 hours (for invasive candidiasis without candidemia) from the time that the SOC blood and/or tissue sample or aspirate/fluid positive for *C. auris* was collected, and any outstanding baseline procedures completed before the first dose of study medication.

All patients (or the patient's LAR) will sign an ICF before any protocol specified procedures that are not indicated by SOC may be conducted. Inclusion/exclusion criteria assessments, medical history, demographics, and Acute Physiology and Chronic Health Evaluation II score will be collected before dosing. When an LAR is used for the initial consent, the patient will be consented during the study as soon as he/she is able to do so.

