4.1 Inclusion Criteria

Patients must meet all of the following criteria to be eligible for study entry:

1. Male or female aged 18 years and above
2. Limited or no treatment options due to resistance, contraindication, intolerance or lack of clinical response to standard of care antifungal therapy, as advocated by the relevant regional/country treatment guidelines
3. Established mycological and clinical diagnosis of candidemia and/or invasive candidiasis from a sample taken <120 hours (for candidemia) or <168 hours (for invasive candidiasis without candidemia) before study qualification:

a. Candidemia criteria

- i. ≥ 1 blood culture positive for yeast/*Candida* spp. identified as *C. auris*;
plus:
 - ii. Clinical signs attributable to candidemia within the 120 hours prior to qualification for the study, to include at least one of the following: (a) fever ($>38^{\circ}\text{C}$), or (b) hypothermia ($<36^{\circ}\text{C}$), or (c) hypotension (SBP $<90\text{mmHg}$ or decrease of $>30\text{mmHg}$);

b. Invasive candidiasis criteria

- i. ≥ 1 specimen (e.g., tissue, aspirate/fluid) sampled aseptically from a normally sterile site culture positive for yeast/*Candida* spp. identified as *C. auris*;
plus:

- ii. Clinical signs attributable to invasive candidiasis within the 168 hours prior to qualification for the study, to include at least one of the following: (a) fever ($>38^{\circ}\text{C}$), or (b) hypothermia ($<36^{\circ}\text{C}$), or (c) hypotension (SBP $<90\text{mmHg}$ or decrease of $>30\text{mmHg}$), or (d) signs associated with organ/site infected with *Candida* (e.g. eye, intra-abdominal).
- 4. Patients with single *C. auris* infection, or mixed *Candida auris* plus other *Candida* spp. (other than *C. krusei*) infection, are eligible for the study.
- 5. Able to have pre-existing intravascular catheters removed and replaced (if necessary)
- 6. Females of childbearing potential with male partners, and males with female partner(s) of childbearing potential, must agree to use 2 forms of highly effective contraception, 1 of which must be a barrier method, throughout the duration of the study and for 90 days following the last study drug administration. Acceptable barrier forms of contraception are condom and diaphragm. Acceptable non-barrier forms of contraception for this study are oral contraceptives (e.g. oral birth control pill, depot, patch, or injectable), abstinence, intrauterine device, and/or spermicide.

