Post-menopausal is defined as amenorrhea for >12 months without an alternative medical cause or documented surgical sterilization (e.g. bilateral salpingectomy, bilateral oophorectomy, or hysterectomy).

True abstinence, when in line with the preferred and usual lifestyle of the patient, is considered a highly effective method only if defined as refraining from heterosexual intercourse during the entire period of risk associated with the study drug treatment. (Periodic abstinence [e.g. calendar, ovulation, symptothermal, post-ovulation methods] and withdrawal are not acceptable methods of contraception)

- 7. Females of childbearing potential must have a negative urine pregnancy test within 96 hours prior to Baseline (i.e. pre-dose on Study Day 1)
- 8. Willing to participate in the study, willing to give written informed consent, and willing to comply with the study restrictions; where permitted by local regulations, written informed consent from a legal authorized representative (LAR) will be obtained for patients who are unable to give consent.
- 9. Male patients must agree to abstain from sperm donation and use condoms with spermicide during sexual intercourse between Screening and at least 90 days after administration of the last dose of study drug. Male patients must ensure non-pregnant female partner(s) of childbearing potential comply with the contraception requirements in Inclusion Criterion 6 (above).

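### Section 8.6 requires pregnancy reporting only to 30 days after study drug, while contraception is required for 90 days, so 60 of the 90 post-dose contraception days carry no duty to report a pregnancy

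*Protocol*

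**What the plan says.** Protocol Section 8.6 triggers reporting when a patient or the partner of a patient "becomes pregnant during the study or within 30 days of discontinuing study drug". A report leads to an exposure-in-utero form and to follow-up until the pregnancy ends.

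Protocol Section 4.1 sets a longer period for contraception. Criterion 6 covers women of childbearing potential and men with such partners, and applies "throughout the duration of the study and for 90 days following the last study drug administration". Criterion 9 covers sperm donation and condom use by men, and runs "between Screening and at least 90 days after administration of the last dose of study drug". The synopsis repeats both criteria.

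Three other provisions bear on the gap:

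- **End of participation.** Section 3.1: "There will be a Follow-up Period of 4 weeks (+4 days) after EOST".
- **Last scheduled pregnancy test.** Section 8.6 ends the tests at "EOST, and 2 and 4 weeks after EOST, or Early Termination for all female patients of childbearing potential". Appendix A agrees.
- **Late safety reporting.** Section 8.3: "All SAEs that the Investigator considers related to study drug occurring after the 30-day follow-up period must be reported to the Sponsor".

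The SAP does not address the period for reporting pregnancies.

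**The concern.** The protocol asks patients and partners to avoid pregnancy for 90 days after the last dose, but asks the investigator to report one only if it begins within 30 days or while the patient is still in the study. The two rules apply to the same people and count from the same event. The protocol gives no reason for the difference.

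What is at stake is safety information on a first-in-class drug that has no approval for fungal disease. A pregnancy that begins in the later part of the contraception period need trigger neither the exposure form nor follow-up of the outcome. Section 8.6 names partners, so it is meant to capture pregnancies fathered by treated men, for whom the precaution lasts at least 90 days.

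**Working it through.** The documents give no figure for this gap, so there is none to reproduce. The check is a comparison of windows.

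**Inputs**

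- Contraception after the last dose: C = 90 days (Section 4.1, criteria 6 and 9; criterion 9 makes this a minimum).
- Pregnancy reporting after study drug: R = 30 days by the written rule (Section 8.6).
- Follow-up after end of study drug treatment (EOST): 4 weeks, plus up to 4 days, so 28 to 32 days (Section 3.1).
- Maximum treatment: 42 days (Section 3.1).

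**Step 1. Does the reference to the study period lengthen the window?** If the last visit is on Day 28, the 30-day rule governs and R = 30. If it is on Day 32, participation runs two days past the 30-day limit and R = 32. This takes EOST as the day of the last dose.

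**Step 2. Uncovered share of the post-dose contraception period**, (C − R)/C:

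- R = 30: (90 − 30)/90 = 60/90 = 66.7%
- R = 32: (90 − 32)/90 = 58/90 = 64.4%

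**Step 3. Sensitivity to the denominator.** Both criteria also apply during treatment, which Section 8.6 covers in full. With T treatment days included, the uncovered share is 60/(T + 90):

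- T = 42 (the maximum): 60/132 = 45.5%
- T = 14 (an assumed short course): 60/104 = 57.7%

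The 60 uncovered days are the same in each case. Only the base changes.

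**Step 4. Does another provision close the gap?**

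- *Scheduled tests.* None is planned after the 4-week follow-up visit.
- *Adverse event collection.* Section 8.1 ends it when participation is complete.
- *Late serious events.* After 30 days, Section 8.3 applies only to serious events the investigator judges related. Pregnancy is not among the seriousness criteria in Section 8.2. Section 8.6 treats certain outcomes, such as stillbirth or congenital anomaly, as serious, so one of these judged related could still reach the sponsor. An uncomplicated pregnancy, or an outcome not judged related, would not have to.
- *Partners.* Section 8.1 defines an adverse event as occurring in a study subject, which a partner is not. Section 8.6 is the only explicit route for partner pregnancies.

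**Step 5. After the change.** With R = 90, the uncovered share is (90 − 90)/90 = 0%.

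**The case against.** The strongest reply is that the two windows serve different purposes. Contraception is a precaution and may carry a margin, whereas reporting is surveillance. Nothing in the documents says that the periods must be equal, and 30 days matches the limit for general serious adverse event reporting. This shows that the difference may be deliberate. It does not explain it, and serious event reporting continues past 30 days for related events while pregnancy reporting has no such extension.

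Four stronger readings are tempting and are not supported:

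- **That the protocol recognises the 90 days as a risk period.** It does not say so. The nearest wording, in the definition of true abstinence under criterion 6, is "refraining from heterosexual intercourse during the entire period of risk associated with the study drug treatment", and no number is attached to it. That the 90 days reflect possible risk is an inference.
- **That in-utero exposure on Days 31 to 90 goes unrecorded.** The documents give no half-life and no reproductive toxicity data, and refer to the Investigator's Brochure for safety information. Whether any exposure remains at that time cannot be judged here.
- **That such a pregnancy breaches the protocol.** Patients agree to use contraception. A conception despite compliance is contraceptive failure.
- **That nothing at all would be reported.** The Section 8.3 duty remains as a partial backstop with no end date.

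Two further points stand in part. The study period in Section 8.6 could be read as lasting until the last visit of the last patient, which would lengthen the window for early enrollees, although the patient's own participation is the more natural reading. The consent pages are not available, so an instruction to patients to report a late pregnancy cannot be called absent. Neither point changes the written limit in Section 8.6.

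**Conclusion.** The mismatch is real, and no other provision closes it. Under Section 8.6, a pregnancy that begins on about Days 31 to 90 after study drug need not be reported or followed, which leaves uncovered about two thirds of the post-dose contraception period. A reader might extend that fraction to the whole period in which contraception is required. That would be wrong, because counting treatment time brings the share down to the values in Step 3 of the working, below one half for a full course.

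The conclusion rests on three assumptions: that the study period means the patient's own participation, that EOST coincides with the last dose, and that criterion 9 is taken at its 90-day minimum. It does not rest on any claim about residual exposure.

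The practical weight is modest. With about 15 patients few pregnancies are expected, and neither the efficacy analysis nor the sample size is affected. The change is still worth making, because it is cheap and uses a period the protocol already contains.

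**What to change.** In Section 8.6, extend the period for reporting pregnancies in patients and partners to the 90 days after the last dose already used in Section 4.1. If the sponsor has grounds for the shorter window, Section 8.6 should state them. At the last visit, ask patients to report any pregnancy, their own or a partner's, that begins within that period. The request would also help with a pregnancy that begins before Day 30 but is recognised only after the last visit. Such a pregnancy is already reportable, but the protocol describes no step for it, and Section 11.4 describes the patient card as giving contact details for serious adverse events. The length of contraception itself is not at issue.

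The cost is about one line in a protocol amendment, with the approval that Section 12.1 requires, and a matching line in the patient information. No visit or test is added. There are two downsides. After the last visit, cases would come to light only by self-report, so capture would be incomplete, particularly for partners. Sites would also have to follow any additional reported pregnancy to its end.
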